### 2.1.2. Statistical analyses

The validation of the DHEQ-fr will consider the study of psychometric properties according to the following plan:

The measure of **acceptability** will be based on the calculation of missing data at the item level and for the overall score; the scale will be considered applicable if the conditions of use show that the cost of implementation is modest, that the acceptability by patients and the medical community is high, and that the time to pass is low.

The **fidelity** of the instrument will be assessed according to two criteria:

- o *Internal consistency* will be assessed by calculating the Cronbach alpha coefficient (Kuder-Richardson  $\alpha_k$ ) and will be studied against the usual recommendations described as follows:  $\alpha_k \geq 0.9$  excellent;  $0.9 > \alpha_k \geq 0.8$  correct;  $0.8 > \alpha_k \geq 0.7$  acceptable;  $0.7 > \alpha_k \geq 0.6$  moderate;  $0.6 > \alpha_k \geq 0.5$  low; and  $0.5 < \alpha_k$  not acceptable.
- o *Test-retest reproducibility*, the ability to produce comparable responses when the measure is repeated while the individual's condition remains stable, will be assessed by calculating the intensity of agreement (for items of a quantitative nature: Lin's coefficient of agreement and for items of a categorical nature: agreement rate: for each item, percentage of identical responses during the test and retest and the Kappa coefficient of agreement (denoted  $k$ ) compared to the following recommendations: no agreement ( $k < 0.2$ ), low agreement ( $k$  0.2 to 0.4), moderate agreement ( $k$  0.4 to 0.6), substantial agreement ( $k$  0.6 to 0.8), or excellent agreement ( $k > 0.8$ ). The overall score will be compared in a test-retest situation by the paired

Student's test in addition to the correlation coefficient (Pearson or Spearman with regard to the statistical distribution) and the Lin concordance coefficient. A graphical representation of Bland and Altman will complete these analyses.

Internal **structure validity** explores the coherence of the internal layout of the questionnaire. This validity will be evaluated by studying the following parameters: for items of a categorical nature: proportion of patients for each of the modalities of each item ('difficulty', denoted  $p$ ), variance of each item (denoted  $p(1-p)$ ), 'item-score' correlations (so-called biserial point correlation coefficient, i.e. correlation between a dichotomous variable and a quantitative variable) and multi-trait matrix of correlation coefficients (inter-item and item-dimension) for the items of a quantitative nature.

A factor analysis will allow us to study the relationships between the modalities of each of the items.

These analyses will be complemented by an item response theory approach; specifically, a Rasch model analysis will be implemented to study the internal structure of the AHS, taking into account inter and intra item variability. The following indicators will be calculated, among others: one-dimensionality, item difficult, DIF (Differential Item Functioning), reliability alpha (PSI: person separation index), fit (overall, outfit, infit).

The DHEQ-fr scores of patients in the HD group will be compared to those of the "control" group by Student's t-test or Mann-Whitney test if the conditions for the application of the t-test are not met. Homoscedasticity will be studied by Fisher-Snedecor test. Results will be expressed in terms of effect sizes and 95% confidence intervals.

The study of the relationships between variables of a quantitative nature (DHEQ-fr, GOHAI, OHIP-49 and 14) will be analyzed by estimation of correlation coefficients (Pearson or Spearman, with regard to the statistical distribution).

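### Does the reversed sign in the lowest Cronbach alpha band leave the internal-consistency scale unusable?

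*Protocol*

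**What the plan says.** Section 2.1.2 of the protocol states that the fidelity "of the instrument will be assessed according to two criteria": internal consistency and test-retest reproducibility. For internal consistency, Cronbach's alpha is to be computed and "will be studied against the usual recommendations described as follows". The list opens with "\alpha_k \geq 0.9$ excellent", "0.9 > \alpha_k \geq 0.8$ correct" and "0.8 > \alpha_k \geq 0.7$ acceptable", continues with *moderate* for 0.6 to below 0.7, and reaches "0.6 > \alpha_k \geq 0.5$ low". It closes with "0.5 < \alpha_k$ not acceptable".

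The next bullet gives a scale of the same kind for kappa. Its lowest band is printed as "no agreement ( $k < 0.2", which points downward as it should. No other section restates or corrects the alpha bands.

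**The concern.** The sixth alpha band should catch what is left below *low*, that is, values under 0.5. As printed, it catches values over 0.5, a range that the five bands above it have already labelled. A literal reader would have to call good results unacceptable and would have no word for poor ones.

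The study exists to validate the DHEQ-fr, alpha is one of only two criteria for its fidelity, and these bands are the only stated scale for reading alpha. The faulty band is also the one that names a failing result. If the labels drove a conclusion, a scale that gives contradictory labels over the range of likely results would matter.

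**Working it through.** There is no formula to reproduce here; the check is one of logic. The inputs are the six inequalities in section 2.1.2, written with *a* for alpha:

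1. *excellent*: a ≥ 0.9
2. *correct*: 0.8 ≤ a < 0.9
3. *acceptable*: 0.7 ≤ a < 0.8
4. *moderate*: 0.6 ≤ a < 0.7
5. *low*: 0.5 ≤ a < 0.6
6. *not acceptable*: as printed, a > 0.5; with the sign reversed, a < 0.5

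**Single values.**

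| alpha | labels as printed | labels with the sign reversed |
|---|---|---|
| 0.30 | none | not acceptable |
| 0.49 | none | not acceptable |
| 0.50 | low | low |
| 0.55 | low and not acceptable | low |
| 0.65 | moderate and not acceptable | moderate |
| 0.75 | acceptable and not acceptable | acceptable |
| 0.85 | correct and not acceptable | correct |
| 0.95 | excellent and not acceptable | excellent |

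**Whole range.** Take alpha from 0 to 1 in steps of 0.001, which gives 1001 values.

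- As printed: 500 values (0.000 to 0.499) have no label, 1 value (0.500) has one, and 500 values (0.501 to 1.000) have two. Sum: 500 + 1 + 500 = 1001.
- With the sign reversed: all 1001 values have exactly one label.

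**Is there a second coherent reading?** Bands 1 to 5 together cover every alpha of 0.5 or more, each once. The only region left without a label is a < 0.5. A sixth band bounded by 0.5 can either fill that region or duplicate what is already labelled. Only the first choice gives a usable scale, and it uses the limit that is printed. The number is therefore right and only the sign is wrong.

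**Does anything depend on the label?** Section 2.1.2 sets no minimum alpha for calling the instrument valid, no rule for dropping items and no action tied to any band. The one conditional judgement in that section, whether the scale counts as applicable, rests on cost, acceptability and completion time, not on alpha. The interim analysis in section 2.1.4 goes ahead with inclusions continuing, whatever alpha turns out to be. The numbers in section 1.1 (216 participants, 60 of them retested) are not linked to the bands anywhere in the text. Alpha itself is calculated the same way under either sign.

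**The case for a change.** The best argument for acting is that a scale fixed in advance should give each value one label, and this one does not. The error is in a complete, legible inequality and contradicts all five bands above it. It sits in the band that identifies failure. It could be copied into the Master II thesis analysis announced in section 2.1.4, or into a later report. Correcting it costs one sign.

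Most of that stands as description. The inequality is wrong as it reads, and nothing elsewhere repairs it. The text was extracted from a PDF, so a conversion error in this one sign cannot be ruled out. However, the neighbouring signs, including those for kappa, came through sensibly, so nothing positively points to one.

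What does not stand is the step from a wrong sign to a risk for the study. To be misled, an analyst would have to accept that an alpha of 0.95 is both *excellent* and *not acceptable*. The absurdity of the literal reading is itself the safeguard. The protocol also presents the bands as customary recommendations and not as a rule devised for this study. If the slip were copied into a report, readers could see it at once, and it would alter no result. The counts of doubly labelled and unlabelled values are all restatements of the same single character, not separate defects.

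**Conclusion.** The printed sign is inconsistent with the rest of the scale, but this is a clerical slip and no change to the plan follows. Read literally, it gives two labels to every alpha above 0.5 and none to any below. Read in the only coherent way, as alpha below 0.5, it gives exactly one label to every value. The effect on the alpha estimate, on any test and on the sample size is nil, and no stated decision rests on the band.

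This rests on two assumptions. The first is that analysts take the last band as the end of a descending list, which its position makes all but certain. The second is that the labels remain descriptive words beside a reported coefficient, as section 2.1.2 has them. If a pass mark for the instrument were tied to these bands, the exact wording would start to matter; the protocol sets none.

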**11/06/2024**

## **1. Study protocol**

### **1.1. Expected duration of participation of individuals**

All participants (n=216) will be invited to a 45-minute visit (test). A second visit will be organized for the 60 patients randomly selected for a 15-day retest.

The maximum duration of participation is therefore 15 days.

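### Do the two-category item statistics and the kappa with no stated weights mishandle DHEQ-fr items that have several ordered answers?

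*Protocol*

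**What the plan says.** Everything on this point stands in Protocol section 2.1.2, except the retest sample, which is in section 1.1.

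- **Internal structure, categorical items.** The description begins "for items of a categorical nature: proportion of patients for each of the modalities of each item" and denotes that proportion by a single p. It then lists the "variance of each item", written p(1-p), and an item-score correlation of point-biserial type, explained as "correlation between a dichotomous variable and a quantitative variable".
- **Internal structure, quantitative items.** These get a multi-trait matrix of inter-item and item-dimension correlations.
- **All items.** "A factor analysis will allow us to study the relationships between the modalities of each of the items". A Rasch analysis with item difficulty and fit is added.
- **Test-retest, by item.** "for items of a quantitative nature: Lin's coefficient of agreement and for items of a categorical nature: agreement rate", which is then spelled out as "for each item, percentage of identical responses during the test and retest and the Kappa coefficient of agreement". Kappa is read against verbal bands, with *low* running from 0.2 to 0.4. No weights are named.
- **Test-retest, overall score.** Paired t-test, correlation, Lin's coefficient and a Bland-Altman plot.
- **Retest sample.** "A second visit will be organized for the 60 patients randomly selected for a 15-day retest".

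The section does not give the number of answers per DHEQ-fr item, whether they are ordered, or whether the items count as categorical or quantitative.

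**The concern.** Two things look wrong.

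First, the statistics listed for categorical items seem not to match their description. A proportion for each answer suggests more than two answers, because for a yes/no item one proportion fixes the other. Yet p(1-p) is the variance of a 0/1 variable, and the point-biserial is explained by the protocol itself as a correlation involving a dichotomous variable. With three or more answers there is no single p, and p(1-p) is not the variance of the item score.

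Second, ordered items with several answers could enter either test-retest branch. Unweighted kappa counts a shift of one step as heavily as a shift from one end of the scale to the other. Lin's coefficient does not. One branch could therefore call an item's reproducibility *low* where the other gives a value near 0.80, and the choice of branch is not written down. Item reproducibility is one of the properties that the validation sets out to establish, so this deserved a check.

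**Working it through.** The protocol states no figure on this point, so there is none to reproduce. The retest sample of 60 and the kappa bands come from the protocol. The number of answers K, how often each is used, and the latent retest correlation are assumptions, varied below.

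**Item variance.** For K equally used answers scored in unit steps, the score variance is (K² - 1)/12. For one answer against the rest, p = 1/K and the indicator variance is p(1-p).

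| K | (K² - 1)/12 | p(1-p) |
|---|---|---|
| 2 | 3/12 = 0.25 | 0.25 |
| 3 | 8/12 = 0.67 | 0.22 |
| 5 | 24/12 = 2.00 | 0.16 |
| 7 | 48/12 = 4.00 | 0.12 |

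The two agree only at K = 2. For larger K, p(1-p) remains the correct variance of the indicator of one answer, and a point-biserial between that indicator and the score is also valid. Only the label that calls it the item's variance fails.

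**Kappa against Lin's coefficient, worked example.** Take 60 pairs, K = 5, equal margins, 28 identical answers and 32 shifts of exactly one step.

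- Unweighted kappa = (observed - chance)/(1 - chance) = (28/60 - 0.20)/0.80 = 0.33, which is *low*.
- Quadratic-weighted kappa = 1 - (mean squared shift)/(2 × score variance) = 1 - (32/60)/(2 × 2.00) = 0.87. With equal margins Lin's coefficient is the same expression, so also 0.87.

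**Latent-normal model.** Cut a normal variable with retest correlation 0.85 into K equally used answers, so that chance agreement is 1/K.

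| K | Identical | Unweighted kappa | Quadratic-weighted kappa = Lin | Chance that unweighted kappa < 0.4, 60 pairs |
|---|---|---|---|---|
| 2 | 0.823 | 0.647 | 0.647 | 0.01 |
| 3 | 0.689 | 0.534 | 0.742 | 0.08 |
| 5 | 0.511 | (0.511 - 0.20)/0.80 = 0.389 | 0.801 | 0.58 |
| 7 | 0.405 | 0.305 | 0.818 | 0.91 |

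**Sensitivity of unweighted kappa.**

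| Setting | K = 5 | K = 7 |
|---|---|---|
| Equal use, correlation 0.80 | 0.33 | 0.26 |
| Equal use, correlation 0.90 | 0.47 | 0.37 |
| Equal use, correlation 0.95 | 0.59 | 0.49 |
| Skewed use (each answer 0.6 times as frequent as the one before), 0.85 | 0.42 | 0.37 |
| Skewed use, 0.90 | 0.50 | 0.44 |

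Under this model, an expected label of *low* for an item with correlation 0.80 or more needs several things together: the categorical branch, no weights, about five or more ordered answers, and limited stability. At five answers and correlation 0.85 the expected value is just under the cut with equal use and above it with skewed use.

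**Which of these conditions does the protocol state?** None. Three cues point towards two-category items: the Kuder-Richardson label on alpha (the 0/1-item form), the formula p(1-p), and the word dichotomous. For such items the formulas are right and all the agreement coefficients coincide. If the items are instead scored on an ordered scale, the quantitative branch is available, with Lin's coefficient and the multi-trait matrix, and it gives the 0.80 and 0.82 of the table.

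**The case for a change.** The best case for a change is that the document's own cues conflict. Asking for a proportion per answer, and a factor analysis of the relations between answers, reads more naturally with several answers than with two. The statistic beside kappa is percent identical, which suggests exact agreement and so an unweighted kappa. Section 2 is itself headed as the statistical analysis plan, so silence cannot simply be passed to another document. A sentence or two would settle the branch before results are seen, at no cost in data.

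Much of this stands. The response format should ideally be written down, and the variance label is loose. But it shows that the text is open, not that it adopts a wrong method. Weighted kappa is nowhere excluded. An analyst with the questionnaire will see at once whether an item is yes/no or scored, and each type has a suitable statistic in the text.

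The possible gain is also small. No item is dropped and no property accepted or rejected on a kappa band. Percent identical is shown next to kappa, so the reader can see how far the coefficient reflects the exact-match rule. Item behaviour is examined again in the Rasch analysis, and the overall score has its own agreement analyses, which the item branch does not touch.

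**Conclusion.** No change to the plan is needed. The arithmetic behind the worry is correct: for five or seven equally used ordered answers at latent correlation 0.85, unweighted kappa would be 0.39 or 0.31, where Lin's coefficient gives 0.80 or 0.82. That contrast rests on an answer count, an item classification and an unweighted kappa, none of which the protocol states. It shrinks with greater stability, and with skewed use of the answers unweighted kappa rises to 0.42 at five answers. With two answers there is no difference at all.

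Read sensibly, the plan sends two-category items to p(1-p), the point-biserial and kappa, and scored items to Lin's coefficient and the multi-trait matrix. Both routes are sound. What is left is missing detail on the response format and on kappa weights, and one imprecise label. In the worst case the effect is confined to the descriptive label of individual items and does not reach the overall score. This judgement assumes that items are classified by their actual response format. If scored items with several answers were in fact reported by unweighted kappa alone, the table above shows how to read the low values.

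### The factor analysis is aimed at response categories, not at how items load on dimensions, so the DHEQ-fr dimensions are checked only indirectly

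*Protocol*

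**What the plan says.** Protocol section 2.1.2 introduces internal structure validity as a property that "explores the coherence of the internal layout of the questionnaire". It then plans four things:

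- **Categorical items:** the "proportion of patients for each of the modalities of each item", the item variance and the item-score correlation.
- **Quantitative items:** a "multi-trait matrix of correlation coefficients (inter-item and item-dimension) for the items of a quantitative nature".
- **Factor analysis**, in one sentence: "A factor analysis will allow us to study the relationships between the modalities of each of the items".
- **Rasch model:** "a Rasch model analysis will be implemented to study the internal structure of the AHS, taking into account inter and intra item variability". The indicators are listed as follows: "The following indicators will be calculated, among others: one-dimensionality, item difficult, DIF (Differential Item Functioning"), then the person separation index and fit statistics.

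The dimensions are not named or counted anywhere in the Protocol, and the number of items is not given. The test-retest plan for scores refers only to the overall score: "The overall score will be compared in a test-retest situation by the paired" Student's test, with correlation and concordance coefficients.

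**The concern.** Factor analysis is the usual tool for asking whether items group as the questionnaire's design says they do. It gives the number of factors, the loading of each item and the fit of the model. Here it sits under the right property but has a different object, the relationships between response categories.

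The plan nevertheless relies on dimensions, because an item-dimension correlation cannot be computed until each item has been assigned to one. If that assignment does not hold in the French version, the study could report a coherent internal structure on the strength of checks that never set the assignment against an alternative. Structural validity is one of the properties the validation is meant to establish, so this evidence should be as direct as the data allow.

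**Working it through.** The Protocol gives no figure to reproduce on this point. The check sets the parts of section 2.1.2 side by side.

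**1. What modalities means.** A few lines before the factor-analysis sentence, the plan counts patients in each modality of each item and calls that proportion the difficulty. A modality is therefore a response category. The factor-analysis sentence uses the same word, so its stated object is categories, not items or dimensions.

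**2. What each planned analysis can show about dimensions.**

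| Planned analysis | What it shows | What it leaves open |
|---|---|---|
| Difficulty, variance, item-score correlation | How each categorical item behaves, and its link to a score | Number of dimensions; item assignment |
| Multi-trait matrix | Items that correlate more with another dimension than with their own | Number of dimensions; fit of a model; items not treated as quantitative |
| Factor analysis of modalities | Patterns among response categories | Item loadings on stated dimensions; fit |
| Rasch one-dimensionality and fit | Whether one trait is enough | How items divide among several dimensions; whether the instrument meant is the DHEQ-fr |
| Cronbach's alpha (under fidelity) | Internal consistency | Dimensionality |

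**3. Whether the pieces add up to a direct test.** The matrix needs dimensions as input. The Rasch check needs a single trait. Using both is coherent if the Rasch model is fitted within each dimension, but the text does not say so. Even then, it would test each dimension on its own and would not compare the whole assignment with a rival, such as one overall factor. The text also names AHS, which appears nowhere else in the Protocol, where one expects the DHEQ-fr. No row of the table yields loadings of the DHEQ-fr items on the assumed dimensions together with a test of how many dimensions there are.

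**4. Why pooling matters.** Both groups complete the DHEQ-fr (section 1.2). If patients with HD score higher on most items, pooling the groups adds a shared component to every inter-item covariance: total covariance = within-group covariance + π(1−π)·dᵢ·dⱼ, where π is the share of patients with HD and dᵢ is the group difference on item i. That component pushes the pooled data towards a single factor. The Protocol does not say which sample the structural analyses use, and the dᵢ are unknown, so the effect cannot be sized.

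**The case against.** The strongest reply is that the sentence describes a joint analysis of the categories of all items, such as multiple correspondence analysis, which is an established method for categorical items. This is the plausible reading, and it disposes of one stronger inference. A reader might infer that the analysis stays within each item, where the categories are mutually exclusive, and so could return only patterns forced by coding. The text does not support that: a factor analysis of one item's own categories would be degenerate, and nothing says it is intended.

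A simulation of the joint analysis confirms that its output depends on the data. The assumed inputs, not taken from the Protocol apart from n, were n = 216, 10 items, 5 equally used categories, loading 0.7 and 200 runs. Mean leading eigenvalues, to two decimals:

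- unrelated items: 0.19 and 0.18;
- two uncorrelated dimensions: 0.32 and 0.28;
- one dimension: 0.51 and 0.23.

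The coding was the same throughout, yet the results differ. The same figures show the limits. With one true dimension the second eigenvalue is still above its level for unrelated items (0.23 against 0.18), so the number of axes is not a plain count of dimensions. With two dimensions correlated at 0.5, the item groups separated poorly.

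A second reply is that the matrix and the Rasch indicators already examine dimensionality. That stands as far as it goes. It would be wrong to infer that no planned analysis bears on the question, and the point is limited to the lack of a direct test.

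A third reply is that the English reads as a translation and that a separate SAP may hold the details. The choice of rotation, estimator and fit limits can indeed be left there and is not criticised. The stated object of the analysis is different: it is in the current text, and if it is only a slip of translation, correcting it costs nothing.

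**Conclusion.** The point holds in a limited form. The factor analysis is stated to relate response categories, and the other structural checks are indirect, so the number of DHEQ-fr dimensions and the item loadings are not directly tested. This rests on modalities having the same meaning throughout section 2.1.2, and on the multi-trait matrix using a real assignment of items to dimensions, which its item-dimension part implies.

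There is no numerical bias to report, and no planned result becomes invalid. The weakness is in the strength of the evidence for structural validity. It goes beyond wording, because a model of the items would answer a question that the planned analyses approach only from the side. It is best classed as a cheap improvement.

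**What to change.** Replace the factor-analysis sentence in section 2.1.2 with text that does the following:

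1. Analyse the DHEQ-fr items jointly, treated as ordinal or with robust estimation.
2. Make the analysis confirmatory against the item-dimension assignment already used for the multi-trait matrix, and list that assignment.
3. Compare this model with a one-factor model.
4. If fit is poor, add an exploratory analysis of the items, labelled as exploratory.
5. State whether patients with HD and controls are pooled.
6. Replace AHS with the name of the instrument meant, and say whether the Rasch model is fitted overall or within each dimension.

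The estimator and fit limits are for the sponsor's statistician to choose, preferably before the data are examined, including for the intermediate analysis in section 2.1.4.

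The cost is a few lines of text and one more analysis. It needs no extra patients, visits or questionnaires. The downside is that fit may be poor, or imprecise if only one group is used, and would have to be reported. How precise it would be cannot be judged here, because the Protocol gives neither the number of items nor the split of the 216 participants between groups.

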#### **Control group**

- Clinical examination performed to confirm the absence of HD;
- Self-administration of DHEQ-fr, GOHAI and OHIP questionnaires.

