## **2. Statistical analysis plan**

### **2.1. Data Analysis Method**

### 2.1.1. General

The statistical analysis will be carried out with the Stata software (version 15, StataCorp, College Station), considering a first-kind bilateral risk of error of 5%.

The sample will be described by associated numbers and percentages for categorical variables and by mean and standard deviation or median and interquartile range for quantitative variables, with respect to their statistical distribution. Normality will be studied by the Shapiro-Wilk test and/or histogram. Graphical representations will be associated with the analyses as much as possible.

Patients will be described and compared between groups at baseline according to the following variables: compliance with eligibility criteria, epidemiological characteristics and clinical characteristics.

A description of the deviations from the protocol, the patients distributed according to these deviations and the causes of abandonment will also be carried out.

The initial comparability of the two arms will be assessed on the main characteristics of the participants and potential factors associated with the primary outcome. Any difference between the two groups on one of these characteristics will be determined according to clinical considerations and not just statistical ones. Comparisons between groups will be made systematically (1) without adjustment and (2) by adjusting for factors whose distribution could be unbalanced between groups despite the matching.

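### The groups are described as matched, but nothing ensures that the matching enters the HD-control comparison of DHEQ-fr scores (minor, cheap to improve)

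*Protocol*

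**What the plan says.** Three statements in the Protocol bear on this point.

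- **Matching and adjustment (2.1.1 General).** "Comparisons between groups will be made systematically (1) without adjustment" and then, as a second step, "by adjusting for factors whose distribution could be unbalanced between groups despite the matching". This is the only mention of matching in the text at hand. The same paragraph says of baseline differences: "Any difference between the two groups on one of these characteristics will be determined according to clinical considerations", and not on statistical grounds alone.
- **The HD-control comparison (2.1.2 Statistical analyses).** DHEQ-fr scores are compared "by Student's t-test or Mann-Whitney test if the conditions for the application of the t-test are not met". The section adds "Homoscedasticity will be studied by Fisher-Snedecor test" and "Results will be expressed in terms of effect sizes and 95% confidence intervals".
- **Test-retest (2.1.2).** "The overall score will be compared in a test-retest situation by the paired" Student's test. This is the only place where the plan names a paired test.

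The type of matching, its factors, its ratio and the split of the 216 participants between the groups are not in the text at hand. They may stand in removed pages, so their absence is not criticised here.

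**The concern.** When groups are matched on factors that predict the outcome, the difference in means varies less from sample to sample than two independent samples would suggest. An analysis that ignores the matching uses a standard error that is too large.

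The tests named for HD versus control treat the groups as independent samples. The adjusted comparison could carry the matching, but its stated criterion is that a factor could be unbalanced. Factors that were successfully matched are the ones least likely to meet that criterion. The rule therefore tends to pass over the variables that the design makes relevant.

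What is at stake is precision. The result is to be expressed as an effect size with a 95% CI, so the width of that interval is what is affected.

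**Working it through.** **Inputs.** From the Protocol: 216 participants in total (1.1) and a two-sided 5% level (2.1.1). Assumed, because the document does not give them: 108 per group, 1:1 pairs unless stated otherwise, SD = 1 in both groups, and a within-pair correlation r of 0.1, 0.2 or 0.3. The plan states no power or precision figure for this comparison, so there is none to reproduce.

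**1. Mean difference, individual matching.**

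The independent-samples half-width is t(0.975, 214) × √(2/108) = 1.971 × 0.1361 = 0.268 SD.

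The paired half-width is t(0.975, 107) × √(2/108) × √(1 − r) = 1.982 × 0.1361 × √(1 − r). The actual coverage of the independent-samples CI is 2Φ(1.96/√(1 − r)) − 1.

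| r | Independent | Paired | Excess width | Coverage of nominal 95% CI |
|---|---|---|---|---|
| 0 | 0.268 | 0.270 | none | 95.0% |
| 0.1 | 0.268 | 0.256 | 5% | 96.1% |
| 0.2 | 0.268 | 0.241 | 11% | 97.2% |
| 0.3 | 0.268 | 0.226 | 19% | 98.1% |

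Coverage above 95% means that the test rejects too rarely, not too often.

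**2. Standardised effect size.** If the effect size means a standardised difference d, its CI also carries the uncertainty in the SD, which pairing does not remove. With n = 108 per group, the approximate variances are:

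- matching ignored: 2/n + d²/(4n);
- pairs used: 2(1 − r)/n + d²(1 + r²)/(4n).

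The ratio of widths is the square root of the first over the second. At d = 1 and r = 0.3 it is √(2.25/1.6725) = 1.16.

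| r | Excess at d = 1 | Excess at d = 2 |
|---|---|---|
| 0.1 | 5% | 3% |
| 0.2 | 10% | 7% |
| 0.3 | 16% | 10% |

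**3. Does the planned adjustment recover the precision?** Take frequency matching in 6 strata that explain 10%, 20% or 30% of the variance. Suppose that the adjusted model holds one unbalanced non-matching factor, which explains 5% of the variance, and leaves the strata out. The residual variance is then 0.95, against 0.85, 0.75 or 0.65 with the strata added. The width ratios are √(0.95/0.85) = 1.06, √(0.95/0.75) = 1.13 and √(0.95/0.65) = 1.21. The CI stays 6%, 13% or 21% wider than it need be, so adjusting for some other factor does not stand in for the matching.

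**4. Unequal SDs.** Controls may vary less in score than HD patients (an inference). With the control SD a fraction k of the HD SD, the excess factor for the mean difference is √((1 + k²)/(1 + k² − 2rk)). At k = 0.5 it is 1.04, 1.09 and 1.15 for r = 0.1, 0.2 and 0.3, somewhat smaller than in step 1.

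**The case against.** The strongest reply is that section 2.1.1 already deals with this. Every group comparison is made both unadjusted and adjusted. The comparability check extends to factors that may be associated with the primary outcome. Differences are judged clinically as well as statistically, and the criterion is that a factor could be unbalanced, not that it has been found so. Nothing bars a matching factor from the model. This stands in part: a reader might infer that the plan excludes the matching factors, or that they would never be selected, and the text supports neither reading. But a clinical judgement about differences is still a rule about imbalance, so it does not ensure that a well-matched factor enters.

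A second reply is that the list of covariates belongs in a separate analysis plan. The list does. The point here is the selection criterion, which this document fixes.

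A third is that the type of matching is unknown, so one cannot say that a paired test applies. That is correct. The paired test named for test-retest is also weak evidence, since it concerns the same person measured twice. For this reason the fix covers both kinds of matching.

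A fourth is that there is no validity error. This stands in full. A reader might infer that ignoring the matching makes the group comparison invalid or raises false positives. The calculation shows the reverse. Controls undergo "Clinical examination performed to confirm the absence of HD" and the HD group has the condition confirmed, so a clear difference is expected and the conclusion may well survive (an inference).

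**Conclusion.** The point holds as a minor, inexpensive improvement. The plan says that the groups are matched, names independent-samples tests, and ties its adjustment to possible imbalance, so the matching may enter neither comparison. Any HD-control comparison that leaves it out has a conservative CI if the matching factors relate to the DHEQ-fr score.

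The size cannot be fixed from the document. The excess widths of 5% to 19% (mean difference), 5% to 16% (d = 1) and 3% to 10% (d = 2) rest on assumed 1:1 pairs, 108 per group, equal SDs and r between 0.1 and 0.3. A weaker relation, or less variable controls, makes them smaller. The cost is precision only.

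**What to change.** Add one sentence to section 2.1.1 or 2.1.2. It should say that the adjusted HD-control comparison always accounts for the matching, whether or not the matching factors look unbalanced. Under frequency matching this means including the matching factors as covariates. Under individual matching it means a matched-set effect or a paired analysis. Report the mean difference and effect size with 95% CI from that analysis next to the unadjusted result, which can stay as planned.

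The cost is a few lines of Stata and no new data. If the matching factors turn out to be unrelated to the score, the price is a few degrees of freedom. The CI is essentially unchanged with 6 strata in the model. With pairs it is under 1% wider for a simple paired test (0.270/0.268 = 1.007 from the rounded half-widths). With a pair effect and one covariate that is unbalanced by 0.3 SD, it is about 2% wider (by simulation).
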